- n. In between study visits, participants will take NA orally at home and will bring their NA with them to each study visit. At study visits, NA should be taken on site. PegIFN α2a should be administered weekly, preferably in the evening by self injection. If desired, participants can also choose to have the weekly administration of PegIFN α2a performed on site irrespective of the time of day.
- o. Complete physical examination, including height (only at screening), body weight, skin examination, and other body systems.
- p. For participants with a risk factor (eg, diabetes or hypertension), an ophthalmic examination at Week 32 of the induction phase should be considered. Any participant experiencing a decrease or loss of vision at any time point during study participation, must have a prompt ophthalmic examination.
- q. Vital signs include supine SBP, DBP, pulse rate, and body temperature.
- r. All ECGs will be read centrally. In addition, on Day 1, the ECG will be collected and assessed locally prior to dosing. ECGs should be completed before any tests, procedures or other consultations for that visit.
- s. A liver ultrasound is recommended every 6 months for HCC screening in high risk populations (ie, participants with a family history of HCC, Asian males >40 years, Asian females >50 years; or African/African American males >40 years).
- t. Biochemistry samples must be taken after fasting for at least 10 hours (6 hours for Week 2 and Week 6) for measurement of phosphate, calcium, creatinine, and lipids. If applicable, participants should bring their study intervention with them to each visit and have that day's intake at the site with food.
- u. The following criteria will trigger additional unscheduled visits: Platelet counts: <100,000 cells/mm3 or <100 GI/L or reduction from baseline by at least 50%; Hemoglobin: Decrease of at least 2 g/dL from baseline or at least Grade 2 (DAIDS); Reticulocytes: Reduction to <0.5% of the RBC count; Neutrophil count: Treatment emergent reduction to at least Grade 2 (DAIDS). (See also to Section 8.3.6.4, Hematologic Abnormalities).

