## 8.3.6. Adverse Events of Special Interest

Events of Special Interest are significant AEs that are judged to be of special interest because of clinical importance, known class effects or based on nonclinical signals. Events of Special Interest that will be carefully monitored during the study include ISRs, ALT/AST elevations, renal complications, hematologic abnormalities, and events related to cholesterol increase (Section 8.2.4, Clinical Safety Laboratory Assessments).

For participants reporting ISRs, ALT/AST elevations, renal complications, and hematologic abnormalities as specified in the DAIDS Toxicity Grading Scale (see Section 10.9, Appendix 9, DAIDS Table), the following should be done.

Note: renal complications and cholesterol increase are AESIs specific for JNJ-6379, which was part of the study intervention up to Protocol Amendment 5. Because most participants who were enrolled before Protocol Amendment 6 was in effect, also received JNJ-6379 as part of their study intervention, the AESIs have not been revised with the removal of JNJ-6379.

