## 8.3.6.4. Hematologic Abnormalities

Mild thrombocytopenia was observed in recently conducted non-clinical toxicology studies with the combination of JNJ-3989 and JNJ-6379. In addition, in a 3-month combination study with 80 rats, 1 rat developed pancytopenia related to bone marrow depletion after 23 days of dosing. Previously, in a 9-month dog study in 24 dogs treated with JNJ-6379 alone, pancytopenia which correlated with a marked increase in plasma cell-like cells in the bone marrow was observed in 1 dog after 60 days of dosing.

No thrombocytopenia or pancytopenia has been observed in the ongoing Jade study (56136379HPB2001) investigating JNJ-6379/Placebo with or without NA treatment. All 232 participants have completed at least 24 weeks of study intervention. In the Phase 1/2a AROHBV1001 study with JNJ-3989, mild transient thrombocytopenia (Grade 1) was observed in 6 out of 84 participants receiving 3 SC injections of JNJ-3989 alone over a period of up to 12 weeks with background of NAs. The transient thrombocytopenia was not considered clinically significant. No thrombocytopenia or pancytopenia was observed in 12 participants when JNJ-3989 and JNJ-6379 were given in combination over a 12-week period.

Based on the non-clinical findings, any relevant abnormalities in hematologic parameters will be carefully monitored as described below:

- Platelet counts: <100,000 cells/mm^3 or <100 GI/L or reduction from baseline by at least 50%
- Hemoglobin: Decrease of at least 2 g/dL from baseline or at least Grade 2 (DAIDS)
- Reticulocytes: Reduction to <0.5% of the RBC count
- Neutrophil count: Treatment emergent reduction to at least Grade 2 (DAIDS)

In case any one of the above criteria are met, a confirmatory visit should be scheduled as soon as possible, preferably within 7 days of the receipt of the initial results. Confirmation of the results will trigger weekly or biweekly (every other week) unscheduled visits until improvement or stabilization of the respective parameter(s). Stabilization is defined as no further significant reduction over two consecutive visits.

In case of confirmed Grade 3 or Grade 4 hematologic abnormalities, discontinuation of treatment with JNJ-3989 and PegIFN- $\alpha$ 2a should be considered. In case of discontinuation, NA treatment should be continued.

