#### Estimating Severity Grade for Parameters not Identified in the Grading Table

The functional table below should be used to grade the severity of an AE that is not specifically identified in the grading table. In addition, all deaths related to an AE are to be classified as grade 5.

PARAMETER	GRADE 1 MILD	GRADE 2 MODERATE	GRADE 3 SEVERE	GRADE 4 POTENTIALLY LIFE-
				THREATENING
Clinical AE NOT identified elsewhere in the grading table	Mild symptoms causing no or minimal interference with usual social & functional activities with intervention not indicated	Moderate symptoms causing greater than minimal interference with usual social & functional activities with intervention indicated	Severe symptoms causing inability to perform usual social & functional activities with intervention or hospitalization indicated	Potentially life threatening symptoms causing inability to perform basic self care functions with intervention indicated to prevent permanent impairment, persistent disability, or death

*Note:* Laboratory abnormalities may have their grading defined in the DAIDS table below, however, all laboratory abnormalities do not necessarily represent an AE. If a laboratory abnormality is considered an AE, the AE need not have the same grade as the laboratory abnormality itself. The AE grade for a laboratory abnormality should be defined by the table above.

	MAJO	OR CLINICAL CONDIT	TONS			
CARDIOVASCULAR						
PARAMETER	GRADE 1 MILD	GRADE 2 MODERATE	GRADE 3 SEVERE	GRADE 4 POTENTIALLY LIFE- THREATENING		
Arrhythmia (by ECG or physical examination) Specify type, if applicable	No symptoms AND No intervention indicated	No symptoms AND Non urgent intervention indicated	Non life threatening symptoms AND Non urgent intervention indicated	Life threatening arrhythmia OR Urgent intervention indicated		
Blood Pressure Abnormalities a Hypertension (with the lowest reading taken after repeat testing during a visit) aged ≥18 years	140 to <160 mmHg systolic OR 90 to <100 mmHg diastolic	≥160 to <180 mmHg systolic OR ≥100 to <110 mmHg diastolic	≥180 mmHg systolic OR ≥110 mmHg diastolic	Life threatening consequences in a participant not previously diagnosed with hypertension (eg, malignant hypertension) OR Hospitalization indicated		

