### 6.1.3. Adverse Events of Special Interest (AESI)

Incidence of treatment-emergent AESI will be summarized by cohort and analysis phase. The AESI include:

- ALT/AST elevations
- JNJ-3989 related Injection Site Reactions
- Renal complications
- Hematologic abnormalities (platelet count, hemoglobin, reticulocytes, neutrophil count)
- Cholesterol increase

The list of all preferred terms belonging to ALT/AST elevations, renal complications, cholesterol increase, and hematologic abnormalities is provided in [Attachment 2](#): Adverse events of special interest list of preferred terms. Injection site reactions will be identified using the eCRF Injection Site Reaction form.

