**Table 5: Laboratory Parameters**

Laboratory Category	Parameters		
Hematology	Platelet count RBC count Hemoglobin Hematocrit	RBC Indices: Mean corpuscular volume Mean corpuscular hemoglobin Mean corpuscular hemoglobin concentration	WBC count with Differential: Neutrophils Lymphocytes Monocytes Eosinophils Basophils
Hematology Coagulation	Activated Partial Thromboplastin Time (APTT) Fibrinogen (FIBRINO) Prothrombin Intl. Normalized Ratio (INR) Prothrombin Time (PT)		
Clinical Chemistry	Sodium Potassium Chloride Bicarbonate Blood urea nitrogen Creatinine Glucose AST/Serum glutamic-oxaloacetic ALT/Serum glutamic-oxaloacetic Gamma-glutamyltransferase (GGT) Total, conjugated and unconjugated bilirubin Alkaline phosphatase Creatine phosphokinase		
	Lactic acid dehydrogenase Uric acid Calcium Phosphate Albumin Total protein Total cholesterol High-density lipoprotein cholesterol Low-density lipoprotein cholesterol Triglycerides Magnesium Lipase Amylase Cystatin C		

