**Table 5: Laboratory Parameters**

Laboratory Category	Parameters	
	Note: Creatinine clearance (eGFR calculated by the CKD-EPI formula) will be assessed. eGFR will also be assessed with the CKD-EPI-Cystatin C equation ( Inker LA et al., 2012 ).	
Routine Urinalysis	Dipstick Specific gravity pH Glucose Protein Blood Ketones Bilirubin Urobilinogen Nitrite Leukocyte esterase	Sediment (if dipstick result is abnormal) RBCs WBCs Epithelial cells Crystals Casts Bacteria
Urine Chemistry (quantitative measurement)	Creatinine Sodium Phosphate	Glucose Protein Albumin
Renal Biomarkers	Retinol binding protein Beta-2-microglobulin	
Thyroid function tests	TSH T4	
Other optional tests in response to ALT flare	Testing for HIV-1 and -2, and hepatitis A, C, and E Testing for CMV, HSV, EBV infection Ig-Electrophoresis	

The laboratory abnormalities will be determined according to the criteria specified in the DAIDS Toxicity Grading Scale (see Clinical Protocol Appendix 9, DAIDS Table) or in accordance with the normal ranges of the clinical laboratory if no gradings are available.

An assessment is treatment-emergent if the toxicity grade/abnormality worsened as compared to the grade/abnormality at baseline; this also includes the shift from abnormally high to abnormally low and vice-versa. Post-reference toxicities/abnormalities are always treatment-emergent with regard to missing toxicities/abnormalities at baseline. The abnormalities 'Abnormally high' and 'Abnormally low' are considered equally important.

For each lab parameter, a worst-case analysis will be performed by using the worst abnormality and/or worst toxicity grade lab value and time point per participant. The worst toxicity case is the value associated to the highest toxicity grade and is derived per parameter and toxicity direction (hypo / hyper). Worst-case will be derived within each phase, including unscheduled assessments. For abnormalities, in case the same subject has both abnormalities (low and high) for the same lab test within the same phase, the participant will be counted in the analysis for both toxicity directions (abnormally high and low).

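### Three of the six hematologic monitoring criteria in Protocol Section 8.3.6.4 have no participant count in the SAP, and reticulocytes are missing from its laboratory table

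*Protocol*

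**What the plan says.** Protocol Schedule of Activities footnotes u (Section 1.3.1) and m (Section 1.3.2) open with "The following criteria will trigger additional unscheduled visits". They then list platelets below 100,000 cells/mm³ or down by half from baseline, next "Hemoglobin: Decrease of at least 2 g/dL from baseline or at least Grade 2 (DAIDS); Reticulocytes: Reduction to <0.5% of the RBC count", and last a treatment-emergent neutrophil fall to DAIDS Grade 2 or worse. Section 8.3.6.4 repeats the list and says "any relevant abnormalities in hematologic parameters will be carefully monitored as described below". A value that meets a criterion leads to a confirmatory visit, and a confirmed value leads to weekly or fortnightly visits. The lead-in to Section 8.3.6 refers to "hematologic abnormalities as specified in the DAIDS Toxicity Grading Scale".

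SAP 6.1.3 makes hematologic abnormalities an AESI and names platelets, hemoglobin, reticulocytes and neutrophils. On identifying cases it says: "The list of all preferred terms belonging to ALT/AST elevations, renal complications, cholesterol increase, and hematologic abnormalities is provided in" Attachment 2.

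On the laboratory side, SAP 6.2.1 says "The laboratory abnormalities will be determined according to the criteria specified in the DAIDS Toxicity Grading Scale", with the laboratory's normal range where no grade exists. Worst cases are taken per phase and include unscheduled samples. SAP 6.2.2 adds low/normal/high shift tables and descriptive statistics of change from baseline at scheduled visits. The hematology row of SAP Table 5 begins "Platelet count RBC count Hemoglobin Hematocrit" and continues with red-cell indices and the white-cell differential. It has no reticulocyte entry.

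**The concern.** The protocol goes to the trouble of defining numerical hematology criteria, two of them relative to the participant's own baseline, and requires extra visits when they are met. The SAP then names the same four parameters as an AESI but counts cases by a route that does not use the criteria. A value that meets a criterion reaches the AESI table only if the investigator also reports it as an adverse event under a listed term, and the protocol's grading appendix warns that "all laboratory abnormalities do not necessarily represent an AE". In an open-label study, that reporting step may vary between sites and between phases.

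At stake is a simple safety question: how many participants met each criterion in induction, and how many in consolidation, when PegIFN-α2a is added? For some criteria no output described in the SAP would answer it.

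**Working it through.** The plan states no figure on this point, so there is nothing to reproduce. The check maps each criterion to the SAP outputs and then uses the DAIDS cut-offs to find which qualifying values go uncounted.

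**Inputs.** The criteria come from Protocol 8.3.6.4. The grades come from Protocol Appendix 9:
- Hemoglobin, men: Grade 1 is 10.0 to 10.9 g/dL; Grade 2 is 9.0 to <10.0.
- Hemoglobin, women: Grade 1 is 9.5 to 10.4; Grade 2 is 8.5 to <9.5.
- Platelets: Grade 1 is 100,000 to <125,000; Grade 2 is 50,000 to <100,000.
- Reticulocytes: no row.

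**Mapping the six components**

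| Component | Counted in a SAP laboratory table? |
|---|---|
| Platelets <100,000 | Yes, identical to Grade 2 or worse |
| Platelet fall ≥50% | No |
| Hemoglobin fall ≥2 g/dL | No |
| Hemoglobin Grade ≥2 | Yes |
| Reticulocytes <0.5% of RBC | No; not in Table 5, no DAIDS row |
| Neutrophils Grade ≥2 | Yes |

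**Hemoglobin.** For a fall of exactly 2.0 g/dL, nadir = baseline − 2.0.
- The nadir stays above Grade 2 when baseline is at least 10.0 + 2.0 = 12.0 (men) or 9.5 + 2.0 = 11.5 (women).
- It has no grade at all when baseline is above 10.9 + 2.0 = 12.9 (men) or 10.4 + 2.0 = 12.4 (women).
- A man at 15.0 who falls to 13.0 meets the criterion ungraded. He needs a fall of 15.0 − 10.9 = 4.1 to reach Grade 1 and more than 15.0 − 10.0 = 5.0 to reach Grade 2.
- A woman at 13.0 who falls to 11.0 is also ungraded. She needs more than 13.0 − 9.5 = 3.5 to reach Grade 2.

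**Platelets** (GI/L). For a fall of exactly half, nadir = 0.5 × baseline.
- Baseline below 200: nadir below 100, so it is counted as Grade 2 or worse.
- Baseline 200 to <250: nadir 100 to <125, so Grade 1 only.
- Baseline 250 or more: nadir at least 125 (250 × 0.5 = 125), so no grade.

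**How many are affected?** The documents give no distribution of hematology values, so a simulation was run on assumptions. Baseline hemoglobin has mean 15.0 (men) and 13.2 (women), platelets mean 230, neutrophil median 3,300, half the participants are men, and the parameters vary independently. Among participants meeting any hemoglobin, platelet or neutrophil criterion, the share with no Grade 2 or worse value was:

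| Assumed on-study falls (mean hemoglobin; platelets; log neutrophils) | Share |
|---|---|
| 0.6 g/dL; 25%; 1.1 | 6% |
| 1.2 g/dL; 30%; 0.9 | 46% |
| 1.8 g/dL; 30%; 0.6 | 78% |

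Reticulocytes were not modelled. Some of these participants would still appear at Grade 1.

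**Comparison within the SAP.** Threshold-based categories are defined for other safety parameters: ALT/AST flares against ULN and nadir (5.3.1.1.9), eGFR falls in 10/30/50% bands (6.2.3.1), confirmed creatinine rises of at least 0.40 mg/dL (6.2.3.1.5) and QTcF change categories (6.2.4.2). Hematology has no equivalent for change from baseline.

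**The case against.** The best reply is that the SAP does follow the protocol. The listed criteria are triggers for visits and monitoring. Section 8.3.6 describes events of special interest as significant adverse events and points to the DAIDS scale, so counting preferred terms beside graded laboratory tables is a legitimate reading. This stands in part: a reader might take the criteria as the AESI case definition, but the protocol never says so. The DAIDS reference cannot be the whole rule either. It also covers ALT/AST, where Section 8.3.6.2 uses other criteria, and DAIDS as reproduced here does not grade reticulocytes.

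Other stronger readings also fail:
- **Most qualifying events go untabulated.** Three of six components are counted, with unscheduled samples included, and the uncounted share depends on inputs that the documents do not give.
- **The SAP ignores change from baseline.** It summarises change descriptively at scheduled visits and gives shift tables. What is missing is a count of participants past the threshold.
- **Reticulocytes appear nowhere.** Attachment 2 contains reticulocyte terms. Their criterion is also an absolute limit, not a fall from baseline.
- **The criteria were written to detect added marrow toxicity from PegIFN-α2a.** Sections 2.2.1.1 and 8.3.6.4 trace them to nonclinical findings, mainly with JNJ-3989 and JNJ-6379. The risk in Section 2.3.2.2.3 is worded for PegIFN-α2a with both agents, and JNJ-6379 has since been removed.

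Finally, the Master Protocol and the Data Presentation Specification, to which the documents refer, were not available and might specify further tables.

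**Conclusion.** The point holds in a limited form. As the SAP is written, no output counts participants with a hemoglobin fall of at least 2 g/dL, a platelet fall of at least 50%, or reticulocytes below 0.5% of RBC. Reticulocytes are named in SAP 6.1.3 but absent from Table 5. Some participants who meet a protocol criterion will be in no DAIDS count and will enter the AESI table only if an adverse event was reported. The reported incidence may therefore be too low as a measure of how often the criteria were met.

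The size cannot be fixed from the documents. The 6% to 78% range shows only that the gap could be trivial or large. The conclusion assumes that no table is specified in documents outside the two reviewed. This is a cheap improvement to the safety reporting, not an error that undermines it.

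**What to change.** In SAP 6.1.3/6.2.2 add one supportive table giving n (%) of participants meeting each of the six Section 8.3.6.4 components, at first occurrence and when confirmed, by cohort and analysis phase. Derive it from all laboratory values, including unscheduled ones, and show it beside the preferred-term AESI table. Add reticulocytes to SAP Table 5. The preferred-term definition can stay as it is; making the laboratory count the primary AESI definition would be a matter of preference that the protocol does not require.

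The cost is a short wording change and one extra table, using measurements that the protocol's triggers already need. The hematologic safety profile may look slightly less favourable.

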# 1.3.2. Schedule of Activities – Consolidation Phase and Follow-up Phase

**Note:** The last visit of the induction phase is equivalent to Day 1 of the consolidation phase. Refer to Section 1.3.1 Schedule of Activities Screening Phase and Induction Phase.

Note: During the follow-up phase, participants who could not stop NA at follow-up Week 2 will have less frequent visits.

Study Phase	Open-label Consolidation Phase						Follow-up a,b													
Consolidation (C)/ Follow up (FU) Week (W)	C W2	C W4	C W6	C W8	C W12 / EOSI / WD°	FU W2	FU W4	FU W8 d	FU W12	FU W16 d	FU W20 d	FU W24	FU W28 d	FU W32 d	FU W36	FU W40 d	FU W44 d	FU W48 / EOS		
C/FU Study Day (Window)	15 +/ 3d	29 +/ 3d	43 +/ 3d	57 +/ 3d	85 +/ 3d	15 +/ 4d	29 +/ 4d	57 +/ 4d	85 +/ 4d	113 +/ 4d	141 +/ 4d	169 +/ 4d	197 +/ 4d	225 +/ 4d	253 +/ 4d	281 +/ 4d	309 +/ 4d	337 +/ 4d		
Study Intervention																				
Administer JNJ 3989		X		X																
Intake of JNJ 6379 (if applicable) II	X	X	X	X																
Dispense of JNJ 6379 (if applicable) II		X		X																
Administer PegIFN α2ae		Wee	ekly																	
Dispense PegIFN α2ae		X		X																
Intake NA (as applicable) e,f	X	X	X	X	X	(X)	(X)	(X)	(X)	(X)	(X)	(X)	(X)	(X)	(X)	(X)	(X)	(X)		
Dispense NA (as applicable) f,g		X		X	X	(X)	(X)	(X)	(X)	(X)	(X)	(X)	(X)	(X)	(X)	(X)	(X)	(X)		
Study intervention accountability		X		X	X	(X)	(X)	(X)	(X)	(X)	(X)	(X)	(X)	(X)	(X)	(X)	(X)	(X)		
Assess NA re treatment criteria, as applicable g							(X)	(X)	(X)	(X)	(X)	(X)	(X)	(X)	(X)	(X)	(X)	(X)		
Safety Assessments																				
Complete physical examination h					X															
Body weight and Symptom directed physical examination	X	X	X	X		X	X	X	X	X	X	X	X	X	X	X	X	X		
Ophthalmic examinationii	(X)	(X)	(X)	(X)	(X)															
Injection site reactions for JNJ 3989 and PegIFN α2a	X	X	X	X	X															
Vital signs i	X	X	X	X	X	X	X	X	X	X	X	X	X	X	X	X	X	X		
Triplicate 12 lead ECG j					X		X													
Liver ultrasound					Xk							Xk						X		
Clinical Laboratory Tests																				
Renal biomarkers 					X															
Hematology m	X	X	X	X	X	X	X	X	X	X		X	X		X		X	X		
Blood chemistry (including liver function tests) n,o,p	X	X	X	X	X	X	X	Xq	X	Xq	Xq	X	Xq	Xq	X	X	X	X		
Blood coagulation		X		X	X	X	X		X			X			X		X	X		

Study Phase	Open-label Consolidation Phase						Follow-up a,b													
Consolidation (C)/ Follow up (FU) Week (W)	C W2	C W4	C W6	C W8	C W12 / EOSI / WD°	FU W2	FU W4	FU W8 d	FU W12	FU W16 d	FU W20 d	FU W24	FU W28 d	FU W32 d	FU W36	FU W40 d	FU W44 d	FU W48 / EOS		
C / FU Study Day (Window)	15 +/ 3d	29 +/ 3d	43 +/ 3d	57 +/ 3d	85 +/ 3d	15 +/ 4d	29 +/ 4d	57 +/ 4d	85 +/ 4d	113 +/ 4d	141 +/ 4d	169 +/ 4d	197 +/ 4d	225 +/ 4d	253 +/ 4d	281 +/ 4d	309 +/ 4d	337 +/ 4d		
Urinalysis r		X		X	X	X t	(X)	(X)	(X)	(X)	(X)	(X)	(X)	(X)	(X)	(X)	(X)	X		
Urine chemistry s		X		X	X	X t	(X)	(X)	(X)	(X)	(X)	(X)	(X)	(X)	(X)	(X)	(X)	X		
Urine pregnancy test (women of childbearing potential only)		X		X	X		X v	X	X v	X v	X v	X v	X v	X v	X v	X v	X v	х		
AFP test p,u					X							X						X		
TSH and T4					X															
Efficacy Evaluations																				
Fibroscan w					(X)							(X)						(X)		
HBV Virology																				
Blood sampling for HBV DNAkk	X	X	X	X	X	X	X	X	X	X	X	X	X	X	X	X	X	X		
Blood sampling for HBV RNA x		X		X	X	X	X	X	X	X	X	X	X	X	X	X	X	X		
Sampling for viral genome sequencing y		X			X		X		X		X		X	X		X		X		
HBV Serology																				
Blood sampling for:																				
Anti HBs and anti HBe					X		X		X			X			X			X		
HBsAg and HBeAg (qualitative)					X				X			X						X		
HBsAg (quantitative)	X	X	X	X	X	X	X	X	X	X	X	X	X	X	X	X	X	X		
HBeAg (quantitative)	X	X	X	X	X	X	X	X	X	X	X	X	X	X	X	X	X	X		
HBcrAg x		X			X		X		X			X			X			X		
Exploratory serology 		X			X	X	X	X	X	X	X	X			X			X		
Clinical Pharmacology Assessments																				
Blood sampling for sparse PK of JNJ 3989, PegIFN α2a and NA aa		Xbb		X bb,e e	(X)cc															
Blood sampling for intensive PK of JNJ 3989, PegIFN α2a and NA (PK substudy) dd				X																
Exploratory Host Biomarkers																				
Whole blood RNA gene expression		X			X							X						X		
Whole blood single cell profiling		X			X	X	X	X	X	X		X			X			X		
Host serum proteins (eg, cytokines)		X			X		X	X	X	X		X			X			X		
Antidrug antibodies (to JNJ 3989 and PegIFN α2a)		X		X	X		X		X			X						X		

CONFIDENTIAL – FOIA Exemptions Apply in U.S. Status: Approved, Date: 25 November 2021

Study Phase			pen-lab lidation		e	Follow-up a,b													
Consolidation (C)/ Follow up (FU) Week (W)	C W2	C W4	C W6	C W8	C W12 / EOSI / WD°	FU W2	FU W4	FU W8 d	FU W12	FU W16 d	FU W20 d	FU W24	FU W28 d	FU W32 d	FU W36	FU W40 d	FU W44 d	FU W 48 / EOS	
C/FU Study Day (Window)	15 +/ 3d	29 +/ 3d	43 +/ 3d	57 +/ 3d	85 +/ 3d	15 +/ 4d	29 +/ 4d	57 +/ 4d	85 +/ 4d	113 +/ 4d	141 +/ 4d	169 +/ 4d	197 +/ 4d	225 +/ 4d	253 +/ 4d	281 +/ 4d	309 +/ 4d	337 +/ 4d	
Immune Monitoring																			
Immune cells (PBMCs) (selected sites only)ff					X	X		X	X			X						X	
Pharmacogenomics (DNA)																			
Epigenetic research (optional)gg		X			X	X			X			X						X	
PRO Evaluations																			
SF 36v2					X							X						X	
HBQOL					X							X						X	
EQ 5D 5L					X							X						X	
PGIC					X							X						X	
Ongoing Participant Review																			
Concomitant therapyhh	X	X	X	X	X	X	X	X	X	X	X	X	X	X	X	X	X	X	
Adverse eventshh,jj	X	X	X	X	X	X	X	X	X	X	X	X	X	X	X	X	X	X	

General Note: The PRO assessments and ECGs should be completed before any tests, procedures or other consultations for that visit.

AFP: Alpha fetoprotein; ALP: alkaline phosphatase; ALT: alanine aminotransferase; AST: aspartate aminotransferase; C: consolidation; CKD EPI: Chronic Kidney Disease Epidemiology Collaboration; d: days; CRF: case report form; DAIDS: Division of Acquired Immunodeficiency Syndrome; DBP: diastolic blood pressure; DNA: deoxyribonucleic acid; ECG: electrocardiogram; eGFR: estimated glomerular filtration rate; EOS: end of study; EOSI: end of study intervention; EQ 5D 5L: 5 Level EuroQol 5 Dimension; FU: follow up; GI: giga; HBcrAg: hepatitis B core related antigen; HBe(Ag): hepatitis B e (antigen); HBQOL: Hepatitis B Quality of Life; HBs(Ag): hepatitis B surface (antigen); HBV: hepatitis B virus; HCC: hepatocellular carcinoma; ICF: informed consent form; ISA: intervention specific appendix; NA: nucleos(t)ide analog; PBMC: peripheral blood mononuclear cells; PegIFN α2a: pegylated interferon alpha 2a; PGIC: Patient Global Impression of Change; PK: pharmacokinetic; PRO: patient reported outcome; RNA: ribonucleic acid; SBP: systolic blood pressure; SF 36v2: Short Form 36 version 2; ULN: upper limit of normal; W: Week; WD: withdrawal.

- a. All follow up study visits are to be scheduled relative to the last dose of JNJ 3989/PegIFN α2a. An unscheduled visit can be performed upon the investigator's discretion, in case of HBV DNA elevations, ALT elevations, other signs of worsening of liver disease, or for any other reason during follow up.
- Participants who withdraw consent during follow up will be offered an optional safety follow up visit.
- c. Participants who discontinue study intervention early will have an early WD visit and will enter follow up unless they withdraw consent. Participants who withdraw consent during study intervention will be offered an optional safety follow up visit to occur on the day of consent withdrawal. For the optional safety follow up visit, assessments are at the investigator's discretion and could be similar to the early WD visit.
- d. Follow up Week 8, 16, 20, 28, 32, 40, and 44 visits are not required for participants who did not complete NA treatment at Follow up Week 2 and for participants who have restarted NA treatment during the follow up period, provided that their HBV DNA and ALT values are stable.
- e. In between study visits, participants will take NA orally at home and will bring their NA with them to each study visit. At study visits, NA should be taken on site. PegIFN α2a should be administered weekly, preferably in the evening by self injection. If desired, participants can also choose to have the weekly administration of PegIFN α2a performed on site irrespective of the time of day. PegIFN α2a should preferably be administered in the evening prior to the sparse PK visit, or alternatively in the morning of the visit on site.

- f. No JNJ 3989/PegIFN α2a will be administered or dispensed during follow up. Administration/Dispensation of NA is only applicable for participants who could not stop NA treatment, or for those who met the NA re treatment criteria. In between study visits, participants will take NA at home and they will bring their NA treatment with them to each study visits, the NA treatment should be taken on site.
- g. If the NA treatment completion criteria are met at consolidation Week 12, treatment with NA will be completed at FU Week 2.
- h. Complete physical examination, including body weight, skin examination, and other body systems.
- i. Vital signs include supine SBP, DBP, pulse rate, and body temperature.
- All ECGs will be read centrally. ECGs should be completed before any tests, procedures or other consultations for that visit.
- k. A liver ultrasound is recommended every 6 months for HCC screening in high risk populations (ie, participants with a family history of HCC, Asian males >40 years, Asian females >50 years; or African/African American males >40 years).
- 1. Urine sample for selected renal biomarkers including retinol binding protein and beta 2 microglobulin.
- m. The following criteria will trigger additional unscheduled visits: Platelet counts: <100,000 cells/mm3 or <100 GI/L or reduction from baseline by at least 50%; Hemoglobin: Decrease of at least 2 g/dL from baseline or at least Grade 2 (DAIDS); Reticulocytes: Reduction to <0.5% of the RBC count; Neutrophil count: Treatment emergent reduction to at least Grade 2 (DAIDS). (See also to Section 8.3.6.4, Hematologic Abnormalities).
- n. Biochemistry samples must be taken after fasting for at least 10 hours (6 hours for Consolidation Week 2 and Week 6) for measurement of phosphate, calcium, creatinine, and lipids. If applicable, participants should bring their study intervention with them to each visit and have that day's intake at the site with food.
- o. Creatinine clearance (eGFRcr calculated by the CKD EPI formula) and eGFRcvs calculated with the CKD EPI cystatin C formula will be assessed.
- p. Intervention emergent ALT/AST elevations (ie, ALT and/or AST ≥3x ULN and ≥3x nadir [ie, lowest value during study participation]), should trigger an assessment of confounding factors (alcohol intake, change in concomitant medication, and comorbidities) and a confirmatory visit, to be scheduled preferably within 7 days of the receipt of the initial ALT/AST results, to repeat laboratory testing of AFP, ALT, AST, ALP, bilirubin (total and direct), INR, albumin, and HBV DNA. Additional tests should be considered based on clinical judgement. For more details and further management guidance, refer to Section 10.6, Appendix 6, Intervention emergent ALT/AST Elevations.
- Liver function tests only.
- r. Urinalysis by dipstick: specific gravity, pH, glucose, protein, blood, ketones, bilirubin, urobilinogen, nitrite, leukocyte esterase, and microscopic analysis if needed. The dipstick reading should be done as soon as possible and in accordance with the manufacturer's recommendation. In case of a positive dipstick result, a urine sample will be set aside for additional examination of the positive parameter at the central laboratory (eg, quantification as applicable).
- s. Urine chemistry sample (quantitative measurement); creatinine, sodium, phosphate, glucose, protein, and albumin.
- t. A urinalysis and urine chemistry sample will be taken at FU Week 2. In case of abnormalities, the tests should be repeated at the following visits until resolution.
- u. Additional samples may be collected for AFP testing in case of ALT flares.
- v. Urine pregnancy tests will be provided to the participants for at home use as necessary to ensure urine pregnancy tests are performed at least every 4 weeks. Results will be reported at the next visit. If a urine pregnancy test is positive, the investigator needs to be informed immediately by the participant.
- w. Only applicable to participants who are enrolled at a site with an on site Fibroscan device.
- x. HBcrAg and HBV RNA samples may be batched and only selected samples may be tested at the sponsor's request. Samples can be used for assessment of other serologic/virologic markers of HBV.
- y. Samples may be sequenced based on the sponsor virologist's request, considering the HBV DNA levels. A sample for viral genome sequencing will be taken at an unscheduled visit for confirmation of virologic flare. In case of a virologic flare, additional samples for viral sequencing may be taken.
- z. Exploratory serology samples may be analyzed at the sponsor's discretion. Samples may be used to assess virologic or serologic markers of HBV.
- aa. All participants will have sparse PK sampling for JNJ 3989, NA, and PegIFN α2a. Bioanalysis of NA and PegIFN α2a is optional at the discretion of the sponsor. Bioanalysis of JNJ 6379 may also be done on samples collected from participants who received JNJ 6379 up to Protocol Amendment 5.
  For all samples, the date and time of the preceding 2 intakes of NA, the date and time of the previous JNJ 3989 administration, the date and time of the previous PegIFN α2a administration, and the date and time of PK sampling should be recorded. PegIFN α2a should preferably be administered in the evening prior to the sparse PK visit, or alternatively in the morning of the visit on site.
- bb. One sample at any time between 2 and 8 hours after JNJ 3989 dosing. Before leaving the study site, the participant's well being should be confirmed.
- cc. Only applicable for the WD visit.

Status: Approved, Date: 25 November 2021

dd. All participants who consent to participate in the intensive PK substudy (optional) will undergo intensive PK sampling at Consolidation Week 8. If necessary (eg, for operational reasons), this visit may be scheduled at Consolidation Week 4. The study intervention should be taken on site and time of dosing should be recorded. Pharmacokinetic samples will be taken predose and 15 minutes, 30 minutes, 1, 2, 3, 4, 6, 8,\* 10,\* and 24 hours post JNJ 3989 dose (\*the 8 and 10 hours postdose samples are optional). All efforts will be made to

- obtain the PK samples at the exact nominal time relative to dosing. However, samples obtained within 20% of the nominal time from dosing (eg, +/ 12 minutes of a 60 minute time point) will not be captured as a protocol deviation if the exact time of the sample collection is noted on the source document and data collection record (eg, CRF).
- ee. Sparse PK sampling is not required for participant with intensive PK sampling at the same visit.
- ff. PBMC samples will be collected at selected sites only. Additional PBMC samples may be taken in case of ALT flares, upon discussion with the sponsor, and may require an unscheduled visit.
- gg. Epigenetic samples are optional and will only be collected from participants who consent separately to this component of the study.
- hh. Adverse events and concomitant medications will be monitored from the time a signed and dated ISA ICF is obtained until completion of the participant's last ISA related procedure.
- ii. Any participant experiencing a decrease or loss of vision at any time point during study participation, must have a prompt ophthalmic examination.
- jj. Includes close monitoring for neuropsychiatric adverse events during the PegIFN α2a treatment period. Participants who develop a neuropsychiatric adverse event during PegIFN α2a treatment, will be monitored closely until the neuropsychiatric adverse event resolves, with frequent (at least weekly) follow up phone calls.
- kk. NA treatment should be re started in accordance with the NA re treatment criteria (see Section 6.6.2, NA Re treatment Criteria and Monitoring After Stopping of NA and Section 10.16, Appendix 16, for guidance after stopping NA treatment).
- Most participants enrolled before Protocol Amendment 6 was in effect, have received JNJ 6379 as part of their study intervention.
- mm. The investigator should consider to re start NA treatment per local standard of care at the EOS visit (Follow up Week 48) for participants who met the NA treatment completion criteria at Consolidation Week 12, who did not re start NA treatment during the follow up phase, and who did not achieve and maintain HBsAg seroclearance. NA will not be provided by the sponsor after the final study visit.

